9.7.6. Secondary endpoints

The new cases of individual autoimmune disease during the specific period (see Section 9.3.2) will be analysed by descriptive statistics per cohort. Incidence rate during the specific period will be computed per cohort for each individual disease as the total number of new cases divided by the total person-year as for the primary endpoint.

In case of more than 10 cases in the exposed female and unexposed female cohorts, a Poisson regression model will estimate the risk ratio and its 95% confidence interval. The Poisson model will include the number of cases in each cohort as the dependent variable, the exposure status as a binary independent variable and the log-transformed total person-year as an offset. Same analysis will be performed for the two male cohorts.

A SCCS analysis of individual disease will be carried out if there are at least 10 cases of disease in the exposed female cohort and during the total of the risk and the control period. The risk period of each disease is the disease specific period : 2 months, 6 months, or 1 year depending on the disease (see Section 9.3.2), the control period is, 22 months, 18 months, or 12 months, respectively. The risk and the control periods are separated by a 6-month buffer period.

These analyses will not be considered as confirmatory analysis.

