For the SCCS analysis, the exposed female cohort will be followed during a total period of 30 months from the first dose. The risk period will be defined as one year after the first dose, including the six months after the last dose when the full three-dose vaccination course is administered. A control period of the same duration will be defined, excluding the periods after subsequent doses. To control for a possible late effect of the vaccine, the control and the risks period will be separated by a six-month buffer period (Figure 2). For analysis of individual diseases, specific risk period could be defined.

light 2 Och control case series analysis	Figure 2	Self-control	case-series	analysis
--	----------	--------------	-------------	----------

Note: all three doses may not have been administered

The SCCS uses each subject as its own control, preventing virtually all potential confounding factors which do not vary with time (e.g. socio-economic status, gender, location) [Whitaker, 2006]. Additionally, fewer cases are usually required, as compared to a case-control design. The control period is chosen subsequent to the at-risk period. Age bias is not anticipated because the follow-up period is short compared to the age effect on incidence of autoimmune diseases (see Table 1).

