9.2.1. The UK HPV National Immunization Programme

The submitted study is in the UK, which is a country with a high Cervarix vaccine coverage. The recommended schedule in the UK for routine HPV vaccination of all girls at 12 to 13 years of age is [DH, 2008; HPA, 2010]:

- Vaccination at this age starts with a first dose of 0.5ml of Cervarix HPV vaccine
- The second dose of 0.5ml follows one to two months after the first dose
- A third dose of 0.5ml follows at least six months after the first dose

The UK has had sufficient Cervarix vaccination coverage to, in theory, enable data acquisition. A public immunisation programme targeting girls between 12-13 years of age including a catch-up programme for young women up to 18 years was undertaken during the academic year 2008/09. A phased catch-up programme for females born 1 September 1991 to 31 August 1995 during the 2008/09 academic year was completed by the end of the 2009/10 academic year. The programme was delivered largely through secondary schools [Crawford, 2009; Sheridan, 2009; Sheridan, 2010]. In the UK public HPV immunization program (12-13 year olds), HPV vaccination coverage in the UK for 2010/11 was 89.0%, 87.6% and 83.8% for the first, second and third dose respectively [Health Protection Agency, 2012]. The recommended age range for the UK programme matches the age range required by the FDA (9-25 years of age) for the post-licensure safety study.

The study population will be composed of female and male subjects, 9 to 25 years of age, registered in the CPRD GOLD.

The exposed cohort will be composed of female subjects vaccinated with at least one dose of Cervarix, with or without other recommended vaccines.

The unexposed historical female cohort will consist of frequency age-matched and practice region-matched female subjects from the period before the introduction of Cervarix. The unexposed concurrent male cohort will consist of frequency age-matched and practice region-matched by one-year classes (15, 16, 17, etc.) male subjects from the

period after the introduction of Cervarix. The unexposed historical male cohort will consist of frequency age-matched and practice region-matched male subjects from the period before the introduction of Cervarix.

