9.3.2. Secondary endpoints

Secondary endpoint is the occurrence of new onset of individual confirmed autoimmune disease during the following specific periods:

- Occurrence of Guillain Barré syndrome (including Miller Fisher syndrome and other variants), and autoimmune haemolytic anaemia within two months following the administration of the first dose of Cervarix;
- Occurrence of idiopathic thrombocytopenic purpura (ITP) within six months following the administration of the first dose of Cervarix;
- Occurrence of multiple sclerosis, transverse myelitis, optic neuritis, other demyelinating diseases (see the two sub-bullets for these diseases in Section 9.3.1), auto-immune uveitis, systemic lupus erythematous (SLE), rheumatoid arthritis (RA), juvenile rheumatoid arthritis (JRA), Still's disease, psoriatic arthritis, ankylosing spondylitis, type 1 diabetes mellitus, auto-immune thyroiditis (including Hashimoto's disease, Graves'/Basedows' disease), and inflammatory bowel / hepatic disease (Crohn's disease, ulcerative colitis and autoimmune hepatitis) within one year following the administration of the first dose of Cervarix.

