9.7.9.2. Self-control case-series

Background

The self-control case-series method (SCCS) was developed to investigate associations between vaccination and acute potential adverse events [Farrington, 1996]. The SCCS is based only on cases, and provides consistent estimates of the relative incidence. It controls implicitly for all fixed confounders, that is to say, confounders that do not vary with time over the observation period, e.g. genetics, location, socio-economic status, gender, individual frailty, severity of underlying disease.

The effect estimate is calculated as the ratio of the rate (or hazard) of events in a given post-exposure period (risk period), to the rate of events in the absence of the exposure (control period).

Risk and control periods

[figure not shown]
For the two co-primary endpoint analysis, the period at risk will be 12 months after the first dose of Cervarix. The control period will also be a period of 12 months after the risk period but separated by a buffer period of 6 months. The new events occurring during the buffer period will not be included in the model (Figure 5). A buffer period is defined to control the risk of late effect of vaccine (risk period for many auto-immune diseases is not clearly defined). We have judged reasonably that the vaccine effect if any will be absent after 18 months.

A sensitivity analysis of the co-primary endpoints will be carried out taking into account individual risk and control periods. For each subject the risk period is the period from the first dose of Cervarix until 6 months after the last dose, and the control period is the period from 6 months after the end of the risk period until month 30. This sensitivity analysis is an SCCS adjusted for the individual variability in the vaccination schedule.

For individual diseases (secondary endpoint), specific risk periods will be defined (Figure 5). SCCS analysis of individual diseases will be carried out only if there are at least 10 cases in the risk and the control periods.

Censoring will not be applied for this analysis, since date of death from the population register will not be available at the time.

Statistical Calculations

The statistical calculation will be done using the specific SAS macro developed by Whitaker et al. [Whitaker, 2006] and available online from http://statistics.open.ac.uk/sccs

Mathematical model

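### For GBS, autoimmune haemolytic anaemia and ITP, the individual-disease SCCS lets time after a late third dose into the control period, contrary to section 9.1.2, which pulls the IRR towards 1

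*Protocol*

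**What the plan says.** Section 9.7.6 of the Protocol sets the individual-disease windows: "The risk period of each disease is the disease specific period : 2 months, 6 months, or 1 year depending on the disease"; then "the control period is, 22 months, 18 months, or 12 months, respectively"; and "The risk and the control periods are separated by a 6-month buffer period".

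Section 9.3.2 anchors the short windows on the first dose: GBS and "autoimmune haemolytic anaemia within two months following the administration of the first dose of Cervarix", and "Occurrence of idiopathic thrombocytopenic purpura (ITP) within six months following the administration of the first dose of Cervarix". All other listed diseases have one year.

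Section 9.7.9.2 says of the buffer: "The new events occurring during the buffer period will not be included in the model". That sentence is written for the co-primary analysis, but it is the only rule given for buffer events.

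Section 9.1.2 describes the control period differently: "A control period of the same duration will be defined, excluding the periods after subsequent doses". It then allows a specific risk period for individual diseases and says nothing about their control period.

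On timing, section 9.2.1 puts dose 2 one to two months after dose 1, and for dose 3: "A third dose of 0.5ml follows at least six months after the first dose".

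**The concern.** GBS, autoimmune haemolytic anaemia and ITP have the shortest risk windows, so their control time starts earliest, at month 8 or month 12. Month 6 is the minimum interval for dose 3, so departures from it can only be later, and a later dose 3 carries its own post-dose window into control time. Section 9.7.6 has no exclusion to prevent this.

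If the vaccine raises the rate after every dose, cases after dose 3 are then counted as background. The denominator of the IRR rises and the estimate moves towards 1. In a safety study that is the direction of false reassurance. Most recipients are concerned: national coverage in sections 9.1.3 and 9.2.1 is 89.0% for dose 1 and 83.8% for dose 3.

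The schedule-adjusted SCCS in 9.7.9.2, where control starts 6 months after the end of a risk period that itself runs to 6 months after the last dose, would avoid the problem. It covers only the co-primary endpoints.

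**Working it through.** **The plan's own figures.** I used the signed-root likelihood-ratio formula with b = ln(IRR), r = risk/(risk + control), D = IRR·r + 1 − r, p = IRR·r/D, A = 2[p·b − ln D], B = (b²/A)·IRR·r(1 − r)/D² and n = (1.96 + 0.842·√B)²/A. At r = 12/24 it gives 193.7, 68.1, 28.8 and 14.9 cases for IRR 1.5, 2, 3 and 5. Table 4 states 194, 68, 29 and 15. With 10 cases the detectable IRR is 8.1 (r = 2/24), 6.0 (r = 6/24) and 8.0 (r = 12/24), matching the 6 to 8 in 9.7.1.2. The stated figures are right and are not part of this point.

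**The windows, in months from dose 1.** Each adds up to the 30-month follow-up in 9.1.2.

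- GBS, haemolytic anaemia: risk 0–2, buffer 2–8, control 8–30 (22 months).
- ITP: risk 0–6, buffer 6–12, control 12–30 (18 months).
- One-year diseases: risk 0–12, buffer 12–18, control 18–30 (12 months).

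**Where later doses fall.** Dose 2 at month 1–2 has a 2-month window ending at month 3–4 and a 6-month window ending at month 7–8. Neither reaches control time. Dose 3 at exactly month 6 has windows 6–8 and 6–12, both wholly in the buffer. For each month that dose 3 is delayed beyond month 6, one month of its window enters control, up to 2 months (2-month diseases) or 6 months (ITP).

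**Size of the dilution.** Assume a rate ratio ρ throughout the disease-specific window after each dose, and 1 otherwise. The whole risk window is then at ρ. If k of the C control months are post-dose time, the control mean is (C − k + kρ)/C, so

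expected IRR = ρ·C/(C − k + kρ).

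For ρ = 3:

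| Dose 3 at | 2-month diseases (C = 22) | ITP (C = 18) |
|---|---|---|
| month 6 | k = 0: 3.00 | k = 0: 3.00 |
| month 7 | k = 1: 66/24 = 2.75 | k = 1: 54/20 = 2.70 |
| month 8 | k = 2: 66/26 = 2.54 | k = 2: 54/22 = 2.45 |
| month 9 | k = 2: 2.54 | k = 3: 54/24 = 2.25 |
| month 12 | k = 2: 2.54 | k = 6: 54/30 = 1.80 |

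For ρ = 5 the values are 110/26 = 4.23 and 90/22 = 4.09 at month 7, and 110/30 = 3.67 and 90/26 = 3.46 at month 8.

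**Cases lost in the buffer.** With doses at 0, 1–2 and 6 months, the risk window holds 2 of 5 or 6 post-dose months for the 2-month diseases (33–40%) and 6 of 12 for ITP (50%). The rest is in the buffer and is dropped. This costs cases but leaves the ratio unbiased, because dropped time enters neither numerator nor denominator.

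**The 10-case threshold in 9.7.6.** 65,000 subjects over 24 months of risk plus control give 130,000 person-years if follow-up is complete. With no effect, Table 1 female GBS rates of 1.1 (UK) to 2.0 (upper US) per 100,000 give 1.4 to 2.6 cases, and UK ITP rates of 2.7 to 4.9 give 3.5 to 6.4. With a fivefold effect and dose 3 at month 6, the ITP count as written is 65,000 × (6×5 + 18)/12 × rate = 7 to 13. With risk time after every dose it is 65,000 × (12×5 + 18)/12 × rate = 11 to 21.

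**One-year diseases.** Doses at 0, 1–2 and 6 months, and the six months after the last, lie within months 0–12. Six-month post-dose time reaches control only if dose 3 is after month 12.

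**The case against.** The 9.1.2 sentence follows directly on the 12-month risk period and speaks of a control period of equal length, which 22 and 18 months are not. It can be read as describing the composite analysis only. Figure 5, which is meant to show the windows by endpoint, is not in the text available to me. This stands in part. The protocol does not say that the exclusion is lifted for individual diseases, and its reason, keeping possible vaccine effect out of the baseline, applies to them equally.

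These analyses are declared non-confirmatory and need at least 10 cases. GBS would rarely qualify, and ITP at UK rates would need a real excess; haemolytic anaemia has no rate in Table 1. That limits the weight of the point but does not make the windows right when the analysis does run. Nor do other analyses repair it: 9.7.5.1 gives incidence after each dose in the cohort analysis and 9.7.9.3 scans individual diseases for clusters, but neither corrects this IRR.

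The documents give no distribution of dose-3 timing, so the actual dilution is unknown. That stands.

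First-dose anchoring is not itself an error. It is the endpoint definition in 9.3.2, and 9.1.2 allows specific risk periods.

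**Conclusion.** The point holds for GBS, autoimmune haemolytic anaemia and ITP. Sections 9.7.6 and 9.1.2 disagree on whether time after later doses may be control time, and following 9.7.6 biases the IRR towards 1 whenever there is an effect and dose 3 comes after month 6. For a true IRR of 3 the estimate is 2.75 or 2.70 at month 7 and 2.54 or 2.45 at month 8. These figures assume an equal rate ratio after each dose, an effect lasting exactly the disease-specific window, and the same dose-3 month for everyone. With dose 3 at month 6, or with no effect, there is no bias.

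Three stronger readings may tempt a reader and are not supported:

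- That every individual-disease SCCS is affected. The one-year diseases are not, for on-schedule doses. Applying a full year after each dose would draw them in (36/14 = 2.57 with dose 3 at month 7), but 9.1.2 works with six months after the last dose.
- That cases dropped in the buffer bias the ratio. They cost power and may keep a disease below 10 cases, nothing more.
- That dilution occurs even with dose 3 at month 6. This needs an effect lasting six months for the 2-month diseases (66/30 = 2.20, with months 8–12 as control), whereas 9.3.2 sets two months for them.

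**What to change.** Reconcile 9.7.6 with 9.1.2. State that each subject's control period excludes all time within the disease-specific window (2 months for GBS and haemolytic anaemia, 6 months for ITP) after any recorded dose. Keep the first-dose risk window as the analysis of the stated endpoint. Correct the equal-duration wording in 9.1.2 so that it applies only where intended, and make Figure 5 agree.

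Add a sensitivity analysis for the three diseases with risk windows after each recorded dose. It recovers cases now lost in the buffer, but needs two caveats: an event may prevent later doses, which breaks the SCCS assumption that exposure does not depend on the event, and section 9.9 warns that vaccination records in CPRD GOLD may be incomplete. Making it the main analysis would be a trade-off rather than a correction.

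The cost is wording and a little code, since full vaccination dates are already an inclusion requirement (9.2.4.1). With doses 1 and 2 on schedule, control time falls by at most 2 of 22 months for the 2-month diseases. For ITP it falls by 1 or 2 of 18 months with dose 3 at month 7 or 8, and by at most 6.

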9.7.7. Exploratory analysis

We will employ the SaTScan software package to investigate temporal clustering of adverse events. Using this package, we will analyze data to test whether the events are randomly temporal distributed. This analysis will be done for each of the four cohorts.

9.7.8. Statistical calculations

All the statistical calculations will be done in SAS 9.2 or higher.

All the statistical tests will be two-sided at alpha level of 0.05.

9.7.8.1. Handling of missing data

Missing data will not be substituted.

9.7.8.2. Descriptive statistics

Age at reference date will be summarized by descriptive statistics per cohort and overall: n of subjects, mean, SD, median, minimum and maximum and compared among the four cohorts using a one-way ANOVA. In case of an overall significant difference, pair-wise comparison using t-test will be carried out.

Exposure to other vaccines (Yes/No) during the year prior to the reference date and during the one year after will be summarized in frequency tables (n, %) per cohort and overall. The four cohorts will be compared using Chi-square test. In case of an overall difference, pair-wise comparison will be carried out using Chi-square test.

All auto-immune diseases will be summarized by descriptive statistics per cohort. The statistics will be computed:

- Number of cases
- Proportion computed as the number of cases divided by the total number of subjects

All the cases of auto-immune disease will be listed with data about exposure status and demographic characteristics.

9.7.9. Statistical models

9.7.9.1. Poisson regression

Poisson regression will be computed using the SAS GENMOD procedure. The dependent variable is the number of events (*Y*). The main model (Model 1) will include the exposure status (exposed (X=1) vs. non-exposed (X=0)) as a binary independent variable, the age-group ([9-18],[18-25]) as a covariate, and the log-transformed total person-time (*PY*) of each exposed and unexposed cohort as an offset.

116239 (EPI-HPV-040 VS UK) Protocol FDA - EMA PASS Final Version 1 $\ln(Y) = \beta_0 + \beta_1 X + \beta_2 Z + \ln(PY)^\circ$

Female cohort model:

The coefficients β_1 and β_2 are the coefficients associated to exposure effect and age-group, respectively. The risk ratio (exposed/unexposed) will be derived as the exponential of the coefficient associated with the exposure status and its 95% Wald confidence interval.

The SAS code is:

PROC GENMOD data=<filename>; MODEL Y= X Z / offset=Ln_PY dist=poisson link=log; RUN;

The same model will be run for comparing the two male cohorts (concurrent vs. historical)

Male cohort model:

 $\ln(Y) = \beta_{0'} + \beta_{1'} X + \beta_{2'} Z + \ln(PY)^{\circ}$

The coefficient $\beta_{l'}$ is the time effect (concurrent vs. historical) in males.

The exposure effect in females adjusted for temporal effect in males model will be:

 $\ln(Y) = \beta_0 + \beta_{11} X_1 + \beta_{12} X_2 + \beta_{13} X_3 + \beta_2 Z + \ln(PY)^{\circ}$

Where:

 X_1 is '1' for the exposed female cohort and '0' for the other cohorts;

 X_2 is '1' for the concurrent male cohort and '0' for other cohorts;

X₃ is '1' for the historical male cohort and '0' for the other cohort.

The Cervarix effect in females adjusted for the temporal effect in males will be computed as :

$$\beta_{1*} = \beta_{11} - (\beta_{12} - \beta_{13})$$

The SAS code is:

PROC GENMOD data=<filename>; Class X (ref=' 1'); MODEL Y= X Z / offset=Ln_PY dist=poisson link=log; Contrast "vaccine adjusted effect in Females" X 1 -1 +1// estimate=exp;; RUN;

Note: X=1 for the non-exposed female cohort, 2 for the exposed female cohort, 3 for concurrent male cohort, and 4 for the historical male cohort.

Sensitivity analysis: A Poisson regression model including, in addition to the exposure and the age-group, other covariates

- Region (class variable: 13 regions defined in CPRD)
- Vaccination during the year prior to reference data (2 classes: yes, no)

• Use of healthcare resources during the previous year (categories will be quartiles computed from all cohorts)

Covariates occurring in less than 5% of the subjects (percentage will be computed over both exposed and non-exposed cohorts) will not be included in the model. If the number of subjects or the number of events is too low in some categories (for example regions), categories could be grouped.

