9.2.3. Number of subjects

For the cohort design, the target sample size is 65,000 subjects for each cohort. Refer to Section 9.5 for a detailed description of the estimation of the sample size.

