9.5. Study size

9.5.1. Sample size for cohort design

The target sample size is 50,000 subjects in each cohort. The relative risk (RR) that would be detected with 80% power and alpha = 0.05 is given in Figure 3 versus the incidence rate in the (Cervarix) unexposed cohort. The detectable difference in incidence rate (= additional cases per 100,000 person-years) is also depicted.

(Method: Comparison of two independent proportions using a likelihood ratio test, PASS 2005)

Cohorts of 50,000 subjects each should allow detection, with 80% power, of a RR between 3.7 and 18.7 for the neuro-inflammatory NOAD (incidence rate between 10 and 1/100,000 person-years) and between 1.6 and 2.0 for other NOAD (incidence rate between 100 and 50/100,000 person-years).

Because of risk of lost to follow-up, the sample size is increased by approximately 30% in each cohort to approx. 65,000 subjects.

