9.7.5. Analysis of co-primary endpoints

9.7.5.1. Cohort analysis

The primary analysis will compare the incidence rates of the primary outcomes of interest between the Cervarix exposed female cohort and the historical unexposed female cohort. Results will be presented as the incidence rate ratio and the incidence difference. Exposed person-time will be defined as the period between the reference date and the earliest of the following events:

- End of study period (defined as 12 months after the reference date);
- Date of de-enrolment from CPRD GOLD;
- Date of unspecified HPV vaccine or Gardasil or Cervarix for unexposed cohort;
- Date of first diagnosis of the outcome of interest.

Incidence rates for auto-immune diseases will be calculated by dividing the number of cases by person-time. A Poisson regression model will estimate the risk ratio and its 95% confidence interval. The Poisson model will include the number of cases in each cohort as the dependent variable, the exposure status as a binary independent variable, the age-group ([9-18],[18-25]) as a covariate, and the log-transformed total person-year as an offset.

Sensitivity analyses

Sensitivity analyses will be performed:

- Incidence rates for NOAD in the exposed cohort will be calculated after each dose by dividing the number of cases by the total person-time. Exposed person-time will be defined as the period between the date of the dose administration and the earliest of the following events:
 - End of risk period (defined as 6 months after each dose);
 - Date of the next Cervarix dose;
 - Date of de-enrolment from CPRD GOLD;

- Date of unspecified HPV vaccine or Gardasil;
- Date of first diagnosis of the outcome of interest.
- Separate analysis will be performed for subjects younger/older than 18 years.
- Analysis including possible confounding factors (if available): other vaccination, age, region, healthcare resource utilization, categorization will be determined based on the available data.
- In case of more than 5% of NOAD with unknown/incomplete date, a sensitivity analysis will be done including these events as occurring during the risk period. This imputation will be done for the four cohorts.
- The same comparison will be done between the two male cohorts. In case of significant difference between these two male cohorts, the primary analysis will be adjusted for time effect other than Cervarix (see Section 9.7.5.1 for the detailed statistical models).

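### The confounder-adjusted sensitivity model drops covariates on pooled frequency alone, so prior-year vaccination could be left out even at almost 10% in one female cohort and 0% in the other

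*Protocol*

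**What the plan says.** Section 9.7.5.1 lists among the sensitivity analyses: "Analysis including possible confounding factors (if available): other vaccination, age, region, healthcare resource utilization". Section 9.7.9.1 turns this into a Poisson model that adds three covariates to exposure and age group:

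- region, in 13 classes;
- "Vaccination during the year prior to reference data (2 classes: yes, no");
- healthcare use in the previous year, in quartiles.

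It then sets an exclusion rule: "Covariates occurring in less than 5% of the subjects (percentage will be computed over both exposed and non-exposed cohorts) will not be included". The next sentence allows sparse categories, such as regions, to be combined.

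The rule has no condition on imbalance between cohorts or on association with the outcome, and no exception for a covariate named in advance. On cohort size, section 9.2.3 states: "For the cohort design, the target sample size is 65,000 subjects for each cohort".

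**The concern.** A covariate confounds the exposure comparison to the extent that it is distributed unequally between the cohorts and is itself related to disease. Pooling the cohorts before computing a frequency averages the imbalance away. A covariate found in one cohort only is the most unbalanced case possible, yet it can fall below the threshold.

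Of the three added covariates, prior vaccination is the one realistically exposed to the rule. Healthcare-use quartiles hold about 25% each by construction. Small regions can be grouped. A yes/no covariate cannot be rescued by grouping.

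Imbalance is possible in this design. The two female cohorts come from periods three years apart (sections 9.1.2 and 9.2.2), they are frequency matched on age and region only, and other vaccines are allowed at any time (section 9.2.4). What is at stake is whether the analysis meant to examine confounding can leave out one of the confounders it was set up to examine.

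**Working it through.** **Inputs from the protocol.** The threshold is 5%, pooled (9.7.9.1). Each cohort has 65,000 subjects (9.2.3). Section 9.5.1 gives, as a yardstick for size: "Cohorts of 50,000 subjects each should allow detection, with 80% power, of a RR between 3.7 and 18.7" for the neuroinflammatory endpoint at 10 to 1 per 100,000 person-years, and "between 1.6 and 2.0 for other NOAD (incidence rate between 100 and 50/100,000 person-years").

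**Assumed, because the protocol does not give them.** The prevalence of prior vaccination in each cohort (p1 exposed, p0 historical), and the covariate-disease rate ratio R, taken as 2 to 3.

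**The plan's own figures.** The 5% threshold has no derivation to reproduce. The yardstick was checked with 50,000 per cohort, 80% power and two-sided alpha 0.05. The normal approximation gives detectable ratios of 3.72 and 18.49 (stated 3.7 and 18.7) and of 1.64 and 1.96 (stated 1.6 and 2.0). The cohort size is 50,000 × 1.3 = 65,000, as stated.

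**Step 1: how unbalanced can a dropped covariate be?** Two female cohorts hold 2 × 65,000 = 130,000 women, and 5% of these is 6,500. The covariate is therefore dropped with up to 6,499 positives. If all are in one cohort:

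- prevalence there is 6,499/65,000 = 9.998%, against 0% in the other;
- pooled prevalence is 6,499/130,000 = 4.999%, below the threshold.

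**Step 2: what does omission leave in the rate ratio?** The residual factor is [1 + p1(R − 1)] / [1 + p0(R − 1)].

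| p1 vs p0 | Pooled | R = 2 | R = 3 |
|---|---|---|---|
| 9.99% vs 0% | 4.995% | 1.0999/1 = 1.10 | 1.1998/1 = 1.20 |
| 0% vs 9.99% | 4.995% | 1/1.0999 = 0.91 | 1/1.1998 = 0.83 |
| 8% vs 1.5% | 4.75% | 1.08/1.015 = 1.06 | 1.16/1.03 = 1.13 |

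With equal cohorts, a pooled figure below 5% means p1 + p0 < 10%. The factor is then largest when p0 = 0, so 1.10 and 1.20 are upper limits for R = 2 and R = 3.

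**Step 3: what does keeping the covariate cost?** Take the extreme split of 9.99% vs 0% with no true exposure effect, and set cases in the historical cohort to 1 unit. The exposed cohort then has 0.9001 units among covariate-negative women and 0.0999 × R among covariate-positive women. Ignoring the other covariates, the adjusted log ratio uses only covariate-negative women, so its variance is proportional to 1/0.9001 + 1 = 2.111.

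- R = 2: unadjusted variance 1/1.0999 + 1 = 1.909; standard error ratio √(2.111/1.909) = 1.05.
- R = 3: unadjusted variance 1/1.1998 + 1 = 1.833; standard error ratio √(2.111/1.833) = 1.07.

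A simulation with 50,000 per cohort at 10 and 100 per 100,000 agrees. The standard error of the exposure effect rose by about 0 to 10%, and the exposure estimate stayed usable even when no case had the covariate.

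**The case against.** The strongest objection is sparse events. Information in a Poisson model comes from cases, not subjects. At the neuroinflammatory rates of 1 to 10 per 100,000 in section 9.5.1, 6,500 covariate-positive women followed for one year yield 0.065 to 0.65 expected cases if the covariate is unrelated to disease. The chance of no case among them is exp(−0.065) = 94% to exp(−0.65) = 52%. With R = 2 it is still 88% to 27%. With no such case, the covariate's own coefficient has no finite estimate. For the other autoimmune diseases, at 50 to 100 per 100,000, the expected count is only 3.25 to 6.5. It would therefore be wrong to say that dropping a rare covariate gains nothing.

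This stands as a real but small cost, and it does not justify the rule. The threshold counts subjects, not events: it keeps a 6% covariate with no cases and drops a 4.9% covariate with several. When no case is covariate-positive, the exposure ratio remains estimable from covariate-negative women, provided both cohorts have cases. At the extreme split it then equals the crude ratio divided by 0.9001, that is, 1.11 times it. At 1 per 100,000, a cohort of 50,000 expects only 0.5 cases, so the model is fragile with or without the covariate.

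Four stronger readings are tempting, and the protocol does not support them:

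- *The adjusted analysis would simply reproduce the unadjusted ratio.* Age group, region and healthcare use stay in the model. Only confounding by prior vaccination is left.
- *The omission would be hidden.* The rule is pre-specified, and sections 9.7.4 and 9.7.8.2 tabulate and test other vaccination by cohort, so a large imbalance would be visible. Those comparisons do not, however, override the exclusion.
- *The rule will remove prior vaccination.* No frequency is given, so this is unknown.
- *The limit is almost 20% in one cohort.* This would follow if all four cohorts were pooled (12,999/65,000 = 19.998%). But section 9.7.9.1 says that quartiles come from all cohorts and words the 5% rule differently, so the two-cohort reading is used here.

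**Conclusion.** The point holds in a limited form. The exclusion rule ignores between-cohort imbalance and could remove a confounder that the protocol names, at a split as extreme as almost 10% versus 0%. The residual factor is at most about 1.10 to 1.20 (0.91 to 0.83 reversed), and 1.06 to 1.13 for a milder split. These figures rest on equal cohorts of 65,000, pooling over the two female cohorts, and an assumed covariate-disease ratio of 2 to 3. A larger ratio would raise the ceiling. Such shifts are well below the detectable ratios of 1.6 to 2.0 and 3.7 to 18.7.

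A reader might infer that the primary result is compromised. It is not: the primary model contains exposure and age group only, so the rule does not touch it. The self-control case-series compares each woman with herself, so imbalance between cohorts in earlier vaccination does not confound it in this way. The matter is minor, but it weakens one sensitivity analysis in the very task it was given.

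**What to change.** Delete the 5% exclusion from section 9.7.9.1. State that prior vaccination (yes/no) and healthcare-use quartile are always kept in the sensitivity model, and that only sparse regions may be grouped, by size and without looking at events by cohort.

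If a threshold is wanted, the minimum change is to apply it within each cohort and drop a covariate only if it is rare in every cohort compared. A covariate at 9.998% versus 0% would then stay in.

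The cost is one sentence changed, one model parameter and a slightly larger standard error for exposure (about 5 to 7% at the extreme split in the calculation above). For the neuroinflammatory endpoint, the coefficient of prior vaccination itself may be inestimable when no vaccinated woman is a case. The plan could say in advance that this will be reported as such and that the exposure estimate is still presented.
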